3 SITE

Volunteer recruitment, evaluation, control, clinical follow-up, hospitalization and processing of the samples to obtain the serum and plasma aliquots applicable to each time point will be conducted at Sanatorio Nuestra Señora del Pilar Research Center (SNSDP). It was authorized by ANMAT to conduct Phase I studies. The authorizing provision is attached in Annex 6 (DI-2019-5344-APN-ANMAT#MSYDS).

Samples will be sent with a numerical code (see section 6.2 MATERIAL PREPARATION AND LABELING) to be able to later identify the patient and the formulation received, with the submission of results. In this way, not only is the anonymity of the volunteer ensured, but also the work done in a blinded manner.

Volunteers will be hospitalized at SNSDP and the serum and plasma samples will be sent to Biosidus S.A. Code described in section 6.2 using a dry ice transport system for biological substances.

All members in the research team agree to adhere to the ethical, legal and administrative standards that govern research on human beings.

4 STUDY DESIGN

Pharmacokinetics, biological activity and immunogenicity will be studied in 20 healthy volunteers starting with a single dose of 1 mg/kg/body weight after administration via intravenous infusion of one (1) dose of:

- Sanofi-Genzyme Fabrazyme®. (Reference Formulation, "R"), or
- Biosidus SA Agalsidase beta (Test Formulation, "T")

This study was conducted under an open, randomized, parallel-arm, balanced, and sequential design. As it is a sequential design, if the statistical analysis of the first 20 volunteers does not show bioequivalence, additional volunteers will be included until the similarity criterion is verified with adequate power.

For volunteers and clinical staff, the study is open. Laboratory determinations will be completed in a blinded fashion, with coded samples.

Below (Figure 1), a study visit scheme is presented:

[figure not shown]

Figure 1 Study Visit Scheme

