SPONSOR	Biosidus S.A. [name] [contact] [contact]
PRINCIPAL INVESTIGATOR	[name] [name] [contact]
CO – INVESTIGATOR	[name]
REGULATORY HEAD	[name]
SITE	Sanatorio Nuestra Señora del Pilar [name]
LABORATORIES	
 • Enzyme Activity Assessment: Biosidus Development Department - [name], Argentina - [contact] - [contact] • Immunogenicity Assessment: Biosidus Development Department - [name], Argentina - [contact] - [contact] • Pharmacokinetic Assessment: Shin Nippon Biomedical Laboratories, Ltd., [name], [contact]; [contact]
PRIMARY OBJECTIVE	Compare the pharmacokinetic behavior of Biosidus Agalsidase beta and Fabrazyme® (Genzyme) after administration by intravenous infusion of 1 mg/kg over a period of 5 hours of one of the following formulations: - Fabrazyme®, by Sanofi Genzyme (Reference Formulation, "R") - Agalsidase beta, biosimilar developed by Biosidus SA (Test Formulation, "T")

SECONDARY OBJECTIVE	Evaluation of enzyme activity, product safety, incidence of adverse events and tolerance. Evaluation of antibody occurrence.
STUDY DESIGN	Open, randomized, parallel-arms, balanced, single-dose, and sequential
DISCONTINUATION SCHEDULE	The sponsor and investigators may independently discontinue the study at any time at the sole possibility or occurrence of a serious adverse event or situation that could affect the volunteer's health.
NUMBER OF VOLUNTEERS	A total of 20 (twenty) male volunteers will initially be included. As it is a sequential design, if the statistical analysis on the first 20 volunteers does not demonstrate bioequivalence, an additional number of healthy volunteers to be determined will be included to verify the similarity criterion with adequate power.

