PHARMACOKINETICS AND BIOLOGICAL ACTIVITY BETWEEN FORMULATIONS	
 - AUC_{0-12h}: area under the serum concentration curve between time 0 and 12 hours. - $AUC_{0-\infty}$: area under the serum concentration curve, as a result of the extrapolation between time 0 and infinite time. - C_{max}: maximum serum concentration of agalsidase beta. - T_{max}: time to maximum serum concentration for agalsidase beta. 
The difference between the T_{max} of the test formulation and that of the reference will be analyzed, and the drug elimination rate constant (Kel) and half-life ($t_{1/2}$) in the body will be calculated.
 
Summary measures (arithmetic and geometric means, standard deviation, CV% and range) for each formulation, as well as the individual results of each volunteer will be presented.

STATISTICAL ANALYSIS:	
SAMPLE SIZE CALCULATION:
 
The sample size ($n: 20$) was established based on data from the literature. As it is a sequential design, if the statistical analysis on the first 20 volunteers does not demonstrate bioequivalence, additional volunteers will be included for the eventual demonstration of bioequivalence with adequate power.

ANALYSIS PLAN	
COMPARATIVE PHARMACOKINETIC ANALYSIS BETWEEN FORMULATIONS
 
 - ABC_T / ABC_R: Ratio between the area under the curve for the Test formulation and the area under the curve for the Reference formulation. For log transformation, the 90% confidence interval of the AUC ratio (for AUC_{0-120h} and $AUC_{0-\infty}$) should be within the range of 0.80-1.25. - $C_{max\ T} / C_{max\ R}$: Ratio between the C_{max} of the Test formulation and C_{max} of the Reference formulation. For logarithmic transformation, the 90% confidence interval of the C_{max} ratio should initially be within the range of 0.80-1.25. 
COMPARATIVE ENZYME ACTIVITY ANALYSIS BETWEEN FORMULATIONS
 
 - Variation in the enzymatic activity for agalsidase beta in the sample at the end of infusion (5 h) compared to baseline (pre-infusion). For logarithmic transformation, the 90% confidence interval of the C_{max} ratio should initially be within the range of 0.80 -1.25. 
For an estimation of the pharmacokinetic parameters, specific pharmacokinetic computer softwares will be used (WinNonlin

Professional Edition, version 5.2.1 (2008).

Possible inter-subject and inter-treatment differences will be studied using ANOVA.

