4.2 CODE UNBLINDING IN BLINDED STUDIES

This study is open to clinical staff, and is only blind for measurements to be made in the laboratory, which will be further carried out, when all the study samples are collected. Therefore, both the sponsor and the principal investigator will know the treatment received by each volunteer. The pharmacokinetic, enzyme activity and immunogenicity samples will be blind during dosing, and will be sent to the relevant laboratories presenting only the identification code of each subject.

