5 CRITERIA FOR SCREENING VOLUNTEERS

5.1 POPULATION

In order to be selected and included in the study, volunteers must meet all the screening and inclusion criteria and none of the exclusion criteria.

The number of subjects to be included in the study will be a total of 20 male volunteers. As a sequential study, additional volunteers may be included.

Those volunteers who meet all the inclusion criteria and none of the exclusion criteria will be incorporated into the study, after having explained the purpose of the clinical trial and having signed the informed consent for participation.

Presence of the following inclusion criteria and absence of exclusion criteria must be verified by the Principal Investigator in the medical record and in the applicable form in the CRF book of each subject.

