7.1.1 Comparative pharmacokinetic analysis between formulations

ABC_T/ABC_R : Ratio between the area under the curve of each test formulation and the area under the curve of the reference formulation.

For logarithmic transformation, the 90% confidence interval of the AUC ratio (for $ABC_{0-120\text{ h}}$ and $ABC_{0-\infty}$) should be within the range of 0.80-1.25.

$C_{max\ T}/C_{max\ R}$: Ratio between the C_{max} of each Test formulation and C_{max} of the Reference formulation. For logarithmic transformation, the 90% confidence interval of the C_{max} ratio should be first within the range 0.80-1.25 (80% to 125%). Considering the high intra-individual variability of this pharmacokinetic parameter, if a variability > 30% is confirmed, this interval for the C_{max} may be extended to 0.75-1.33 (75-133%).

The FDA assumes that the test product is considered bioequivalent to the reference product if the 90% confidence interval (CI) of the geometric mean ratio of AUC and C_{max} between the test product and the reference product fall within the range 80-125%, even though the application of such criterion to drugs with high variability is controversial and regulatory agencies as strict as the FDA use different criteria. In Argentina, renowned specialists such as R. Bolaños, MD and S. Giarcovich, MD have analyzed the current status of the bioequivalence in the world proposing the most appropriate study designs.

Globally, drugs with high intra-individual variability are considered to be those with a coefficient of variation (CV) greater than 30% in pharmacokinetic parameters such as C_{max} and AUC. Different strategies have been tested given the high variability issue and in order to meet the conventional bioequivalence principles (90% CI 80-125). One has been to significantly increase the number of volunteers, sometimes to an unfeasible number, although this procedure does not guarantee that the results will fall within that equivalence interval. In this regard, there are reference products with high variability that are not capable of demonstrating bioequivalence with themselves. Additionally, the increase in volunteers to minimize variability poses an ethical problem, since we expose a greater number of healthy individuals to drugs that involve a risk in order to meet the bioequivalence criteria, which have been arbitrarily established. Other approaches have additional problems.

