7.2 PHARMACODYNAMIC ANALYSIS OF RESULTS

As an estimator of agalsidase beta biological activity, blood samples will be drawn to determine the variation in the agalsidase beta enzyme activity of the end-of-infusion sample (5 h) compared to baseline activity (pre-infusion).

Ratio of activity variation in both groups to be close to the unit and that the 90% CI is within the range 0.8 to 1.25 will be taken as bioequivalence criterion.

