10 STATISTICAL CONSIDERATIONS AND ANALYTICAL PLAN. SAMPLE SIZE CALCULATION

A recent study with JR-051, the first agalsidase beta biosimilar to be approved in Japan, was conducted in 20 volunteers (10 per treatment group), based on the fact that previous studies with this molecule assumed the geometric mean of C_{max} and ABC_{0-24} with a value of 1.0 and a coefficient of variation of 0.15.

Therefore, with a power = 0.80, significance level $\alpha = 0.05$, and a limit for accepting bioequivalence where the 90% confidence interval of the AUC ratio (for AUC_{0-120h} and AUC_{0-24}) should be within the range of 0.80-1.25 9 volunteers per group are required for the study, estimating the possibility of 1 volunteer lost to follow-up per group, the sample size was calculated in 20 volunteers.

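### The sequential extension has no error control: no adjusted confidence level, maximum N, number of looks or failure rule, so alpha = 0.05 holds only for a single analysis

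*Combined protocol and SAP*

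**What the plan says.** Section 4 (Study Design) calls the trial sequential. If the first 20 volunteers do not show bioequivalence, "additional volunteers will be included until the similarity criterion is verified with adequate power". The Protocol Summary puts it differently. Under Number of Volunteers, "an additional number of healthy volunteers to be determined will be included to verify the similarity criterion with adequate power"; under Sample Size Calculation, "additional volunteers will be included for the eventual demonstration of bioequivalence with adequate power". Section 5.1 says: "As a sequential study, additional volunteers may be included". The Summary and Section 5.1 fit a single extension, while the Section 4 wording reads as open-ended.

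The decision criteria use one confidence level throughout:

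- **Section 7.1.1:** "For logarithmic transformation, the 90% confidence interval of the AUC ratio" must lie within 0.80-1.25. Cmax has the same criterion, with possible widening to 0.75-1.33 if variability exceeds 30%.
- **Section 7.2 (enzyme activity):** "the 90% CI is within the range 0.8 to 1.25 will be taken as bioequivalence criterion".
- **Section 10:** alpha 0.05, power 0.80, ratio 1.0 and CV 0.15 lead to "9 volunteers per group are required for the study, estimating the possibility of 1 volunteer lost to follow-up per group", hence 20 in total.

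No section gives an adjusted confidence level, the number or timing of looks, a sizing rule for the extension, a maximum N, a rule for combining stages, or an outcome if the extension fails. The discontinuation and termination provisions (Sections 4.3 and 13) concern safety or decisions by the sponsor, the investigator, the ethics committee or the authority, not statistical failure. On the timing of laboratory measurements, Section 4.2 says: "which will be further carried out, when all the study samples are collected".

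**The concern.** A 90% interval inside the limits is two one-sided tests at 5% each, and it limits the risk of declaring a non-equivalent product bioequivalent to 5% for one analysis. A second test on pooled data after a failed first test adds a further chance of a false pass. On a literal reading of Section 4, the trial never reaches a point at which bioequivalence is declared not shown.

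This affects the primary conclusion: a pass after extension could not be reported as a 5%-level result. It also cannot be repaired once first-stage results are known. Under Section 4.2 the sponsor and principal investigator know each volunteer's treatment, so an unwritten extension rule could be chosen with results by arm in view.

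**Working it through.** **1. Reproducing the plan's sample size.** Inputs from Section 10: ratio 1.0, CV 0.15, limits 0.80-1.25, alpha 0.05, power 0.80. The arms are parallel, so the CV is taken as between-subject.

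- Log-scale SD: σ = √ln(1 + 0.15²) = √0.02225 = 0.149. Limits: ±ln 1.25 = ±0.223.
- Standard error with n per group: σ√(2/n). For n = 9 this is 0.149 × 0.471 = 0.070.
- Bioequivalence is declared if D ± t(0.95; 2n−2) × s√(2/n) lies within ±0.223, where D is the difference in log means and s the pooled SD.
- Exact power, integrating over the distribution of s: 0.769 (n = 8), 0.836 (n = 9), 0.884 (n = 10).

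The smallest n reaching 0.80 is 9. Adding one per group gives 20. The plan's figure is therefore correct for a single analysis with 0.05 per one-sided test.

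**2. False-bioequivalence rate when the analysis is repeated.** This is a Monte Carlo simulation of the same test at a true ratio of 1.25. Assumptions not in the documents: stages pooled, 90% interval kept at each look, limits 0.80-1.25 throughout, and one parameter at the limit while the others pass easily (the worst case). The re-sized extension uses the first-stage CV, 80% power, an assumed ratio of 1.0 or 0.95, and a cap of 40 per group.

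| Rule, starting from 10 per group | CV 0.15 | 0.20 | 0.25 | 0.30 | 0.40 |
|---|---|---|---|---|---|
| Single look | 5.0% | – | – | 2.1% | – |
| One extension, re-sized | 6.4-6.9% | 7.3-7.8% | 7.6-7.9% | 6.7-6.8% | 5.2-5.3% |
| One fixed extension of 10 per group | 8.1% | – | 7.6% | 6.4% | 3.0% |

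(A dash marks a setting not reported.) For the fixed extension at CV 0.15, 5.0% pass at the first look and a further 3.1% fail first and pass second: 5.0 + 3.1 = 8.1%. If extensions of 10 per group repeat, the rate is about 10% at three looks and 13% at five. Starting from 9 evaluable per group, the re-sized extension gives 6.6-7.1% at CV 0.15 and up to 8.1% at CV 0.20.

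**3. AUC and Cmax both at 1.25.** Both must pass at the same look. At CV 0.15 with one fixed extension, the rate is 2.0%, 3.2%, 4.2%, 5.3% and 6.1% for correlations of 0.5, 0.7, 0.8, 0.9 and 0.95.

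**4. An adjusted level.** One-sided alpha 0.0294 at both looks corresponds to an interval of 1 − 2 × 0.0294 = 94.12%. With one fixed extension the rate is 4.9% at CV 0.15 and 3.2% at CV 0.30. It was at most 4.9% in every one-extension setting run. Adding stage as a factor moved the error rates by at most 0.03 points.

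**The case against.** The strongest counter-argument is about size. On the Protocol Summary's wording, a single extension sized for adequate power raises the rate at CV 0.15 only to between 6 and 7%. The 8.1% needs a fixed 10 per group, which no section states. If the Section 10 assumptions hold, an extension is needed in only 12-16% of trials (1 − 0.884 and 1 − 0.836). Five looks would mean 100 volunteers, which sits badly with admissions of two at a time and a study of about six months. Requiring AUC and Cmax to pass together brings the rate below 5% in several scenarios.

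All of this is fair as to size. It does not supply the missing rule. Practical limits are not a prespecified cap, and adequate power limits false failures rather than false passes. The joint requirement does not help when one parameter sits at the limit: with the second at 1.10 and correlation 0.8, the rate is still 8.1%.

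Two further points stand as limits. Cmax widening was not modelled, so the high-CV figures may not describe Cmax under this plan; the CV 0.15 result is unaffected. And the Section 4.2 wording could mean the samples of the first 20 only, but as written it leaves the timing of the first analysis unclear and needs reconciling.

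**Conclusion.** The concern holds, and the plan must be changed. The sample size of 20 is right for one analysis; the defect is in the sequential rule. With unadjusted 90% intervals on pooled data, even a single extension takes the worst-case false-bioequivalence rate at the plan's own CV above 5%. The exact excess depends on extension sizes and a pooling rule that the plan does not state. Some settings stay below 5%, such as a fixed extension at CV 0.40 or two less strongly correlated parameters both at the limit, but a 5% claim must also cover the case of one limiting parameter. The main ground for the change is that the primary decision rule is undefined after the first look; the modest size of the single-extension excess does not remove that.

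**What to change.** Before the first 20 are analysed, write a capped, error-controlled rule into Section 4. One option:

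> Bioequivalence is tested on the first 20 volunteers with a 94.12% confidence interval (one-sided alpha 0.0294). If it is not shown, one extension only is allowed. Its size is computed from the first-stage CV, a fixed assumed ratio and 80% power at alpha 0.0294, up to a stated maximum N. Both stages are pooled, with stage as a factor, and tested with a 94.12% confidence interval. If this fails, bioequivalence is not shown.

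Another rule is acceptable if it is shown to hold 5%. The text should also name the parameters that must pass to avoid the extension, the parameter whose CV sizes it, and the look at which any Cmax widening is decided.

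Carry the change through the Protocol Summary and Sections 5.1, 7.1.1, 7.2 and 10, so that no 90% criterion contradicts it. In Section 4.2, state that first-stage samples are measured before the extension decision and how laboratory coding is kept afterwards. Annex 4 allocates only volunteers 1-20, so provide for allocating an extension.

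The cost is wording plus first-look power. All figures below are for one parameter; unless stated, CV is 0.15 and the ratio 1.0.

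- **First look, 9 evaluable per group:** power falls from 83.6% to 73.0%, and the chance of needing the extension rises from 16% to 27%.
- **First look, 10 evaluable per group:** power falls from 88.4% to 80.1%. Keeping 0.80 after one loss per group would need 11 per group, 22 in total.
- **Overall two-stage power, cap of 40 per group:** 92-95% from 9 per group and 93-96% from 10. At ratio 0.95 it is 82-87% and 84-88%.
- **Higher variability, from 10 per group with that cap:** about 75-82% at CV 0.30 and 48-49% at CV 0.40, so the sponsor should choose the cap deliberately.

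Restate the power in Section 10 on the adopted rule.

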4.1 RANDOMIZATION PROCEDURE

Randomization to the study will be performed by chance, using a table of random numbers, using the RANDOM software of Randomness and Integrity Services Ltd. Premier Business Centres, [name]. It will be carried out in a balanced way in the anthropometric variables between both arms.

Annex 4 contains the randomization table, which indicates the treatment (R or T) assigned to each patient.

4.2 CODE UNBLINDING IN BLINDED STUDIES

This study is open to clinical staff, and is only blind for measurements to be made in the laboratory, which will be further carried out, when all the study samples are collected. Therefore, both the sponsor and the principal investigator will know the treatment received by each volunteer. The pharmacokinetic, enzyme activity and immunogenicity samples will be blind during dosing, and will be sent to the relevant laboratories presenting only the identification code of each subject.

4.3 STUDY DURATION AND DISCONTINUATION SCHEDULE

The study duration is approximately 6 months since the approval by the ANMAT, for the recruitment of volunteers, study conduction, analysis of results and final report preparation. Times for completion are subject to the COVID-19 Pandemic progress in Argentina, especially in the Province of Buenos Aires, and the availability of beds at SNSP.

The sponsor and the investigators independently may discontinue the study at any time at the possibility or occurrence of a serious adverse event or situation that could impact on the volunteer's health.

4.4 STUDY COURSE AND PROCEDURES

The study will be conducted by staff trained in the Good Clinical Practice (GCP) Standards by the International Council for Harmonization (formerly International Conference on Harmonization), in compliance with ANMAT Regulation 6677/10.

Principal Investigator, [name] will be responsible for conducting this study.

4.4.1 Procedures to be made at each Visit

VISIT I (Screening)

After signing the informed consent, each volunteer will undergo a physical examination that will include: medical history, neurological semiology, cardiovascular, (ECG, blood pressure, chest x-ray). Volunteers weight will be measured, taking this body weight to adjust the dose should they enter the study. Lab tests will also be done within 30 days, including:

- CBC
- Erythrocyte sedimentation
- Uremia
- Blood glucose
- Uricemia
- Gamma GT
- LFT
- Quick time
- KPTT
- Platelet count
- Hepatitis B and C and HIV screening tests
- Urinalysis for screening drugs of abuse (cannabinoids and cocaine)
- Serum electrolyte panel
- Complete urinalysis
- PCR for COVID-19
- Serum creatinine
- Glomerular filtration rate (GFR)
- Urine protein

In the event that outliers are detected, volunteer will be contacted by phone, email or by mail to arrange a new visit where he/she will be informed about the reasons why he/she cannot participate and will also be instructed to see an applicable medical specialist.

VISIT II (Hospitalization)

During this visit, volunteer will receive the formulation randomly assigned. Volunteers must come to the clinic the day before, at 8:00 p.m. and the infusion will begin at 8:00 a.m. the following day, with the volunteer in fasting state.

In this instance, the Principal Investigator will ensure whether volunteers meet the conditions to proceed with the drug infusion (interrogation and physical examination).

There will be a staggered hospitalization of two volunteers at a time.

After the hospitalization of the first two volunteers (1 Reference volunteer and 1 Test volunteer), a week will be allowed to admit the next two volunteers. At the end of each hospitalization, volunteers will be evaluated for AE occurrence. If no AEs that jeopardize the participant's safety occur, the next volunteers will be hospitalized according to the randomization table at the time intervals deemed appropriate by the Principal Investigator.

To draw blood samples and avoid multiple punctures, an abbocath-type intravenous line with a three-way stopcock will be placed in the arm contralateral to the one used for agalsidase infusion. Through it, all blood samples will be drawn during hospitalization.

At each time point, 30 mL of blood will be drawn, which will be placed in adequate tubes to obtain serum or plasma, as appropriate (for example, up to 500 mL of blood is drawn from a volunteer blood donor at a time and without consequences for him/her).

Samples to be obtained from each volunteer will be drawn from the contralateral arm to which the infusion of the experimental drug is being made.

After verifying its correct operation, the pre-dose sample (hour 0) will be drawn. Next, the intravenous administration of the corresponding infusion will begin according to the order of randomization.

Sampling times during Visit II will be the following:

1. For pharmacokinetic analysis: predose (0 hour), 1 h, 3 h, 5 h, 5,5 h, 6 h, 7 h, 8 h, 10 h, 12 h from the beginning of infusion.
2. For enzyme activity analysis: predose (0 hour), 1 h, 3 h, 5 h, 5,5 h, 6 h, 7 h, 8 h, 10 h, 12 h from the beginning of infusion.
3. For immunogenicity analysis: predose (0 h), 12 h and day 35.

On the study day, volunteers will be allowed to drink fluids freely.

Alcoholic drinks or xanthines will not be allowed (since 48 hours before the test).

No medication (neither allopathic nor homeopathic) will be allowed during the two weeks prior to the study.

Snacks during Visit II:

During hospitalization, volunteers may consume only standardized food, provided by the clinic. No other type of food will be allowed other than that which complies with the guidelines that are developed below:

Meal	Time Schedule	Menu
Lunch	4 hrs after the beginning of the infusion (approximately between 12 and 12:30 p.m.)	A piece of chicken (breast or leg and thigh), with no skin A portion of white rice 500 mL of mineral water 1 sachet of salt 1 small package of crackers 1 apple.
Afternoon snack	8 hrs after the beginning of infusion (approx. 4:00 p.m.)	1 cup of coffee or tea (decaffeinated with 100 mL of whole milk), 2 butter croissants each with 2 cooked ham slices and 2 cheese slices.
Dinner	12 hrs after the beginning of the infusion (approx. 8:00 p.m.)	A piece of chicken (breast or leg and thigh), with no skin A portion of white rice 500 mL of mineral water 1 sachet of salt 1 small package of crackers 1 apple.

VISIT III, IV, V y VI (phone contact):

The principal investigator or the delegated medical staff will contact the volunteer by telephone after visit II to ask about tolerance to medication and the occurrence of adverse events on days 3, 7, 14 and 21 after visit II respectively.

VISIT VII (on-site)

Volunteers will come to SNSDP after 35 days, to complete the end-of-study visit on an outpatient basis in order to assess the patient overall clinical status. The same studies carried out at the initial visit will be repeated.

For the immunogenicity analysis, a serum sample will be collected.

